#### **Exclusion Criteria**

- 1. Patient has unstable cardiovascular condition
- 2. Significant unilateral or bilateral nasal occlusion
- 3. Vigorous physical activity should not be performed within 2 hours of testing
- 4. Inability to provide informed consent
- 5. Pregnancy
- 6. Known contraindication to perform steps of the protocol
- 7. Absence of spontaneous respiration or known contraindication to HVNI
- 8. Inability to use nasal cannula and HVNI therapy
- 9. Agitation or uncooperativeness
- 10. Determined by the clinician to be sufficiently unstable or unsuitable for this study

## IV. Study Design

This will be an efficacy study, performed as a prospective, order-randomized crossover design trial to evaluate the ability of next generation HVNI nasal cannula designs (Unicorn and Prosoft) to effect ventilation and related physiological responses relative to the conventional legacy cannula design. Patients deemed to fit the criteria for inclusion will perform the study procedures for both arms of the crossover design. Completing both arms will compare the next generation cannula designs to the commonly used legacy design for comfort, comparative therapeutic response, and outcomes per the study aims. Patients are expected to complete the study in one session, with appropriate pauses between each nasal cannula design testing procedures. After each of the study arms, the clinicians will complete perception score assessments. The clinical management will otherwise remain unchanged based on site standard of care practice.

Each phase of the study will correspond to a different cannula design. Patients will be enrolled and initially entered into the control/baseline phase with the conventional legacy cannula (control), then will be order randomized to either of the next generation cannula designs (Test: Unicorn, or Prosoft).

- Phase 1 – Conventional Legacy cannula design (Control)

- Phase 2 Next generation cannula design (Test#1) (order randomized)
- Phase 3 –Next generation cannula design (Test#2) (order randomized)

This study design will focus on four distinct segments for each phase: (1) baseline characterization, (2) therapy acclimatization, (3) therapeutic characterization, and (4) VAS for both patient and clinician assessment scores. The baseline characterization for Phase 1 will provide patient background, history, and initial clinical evaluation. For Phases 2 and 3, baseline characterization will only include the initial clinical evaluation, as no further initial evaluation is warranted. The acclimatization period will provide patients time to become accustomed to the HVNI therapy and both designs of nasal cannula design. Titration of therapy (Flow/FiO2) is only expected during Phase 1 (or in the event the patient decompensates and needs adjustment), the legacy cannula, as this study is a comparison of cannula efficacy. For the therapeutic characterization, final patient data for the cannula design will be recorded. Following this, the clinician and the patient will complete the cannula design's VAS perception scores. Primary and secondary outcomes will be completed at the end of each individual phase.

This study will be conducted in an inpatient hospital setting where patient testing can be performed with appropriate medical supervision and staff training to maintain patient safety. All respiratory interventions will be tracked during the study window for each patient.

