Upper airway purge is important to alveolar gas exchange as the gas that is drawn to the respiratory regions of the lungs comes from the dead space or anatomical reservoir created by the flush, in the same way that oxygen conservation masks (re-breathers) can incorporate reservoir bags to reduce the bulk flow requirements from the oxygen source to achieve the same oxygenation effect.  Based on mathematical modeling, physiologic studies and clinical observations, a flow rate of 4 to 8 L·min through Vapotherm's neonatal cannulae, or 25 to 40 L·min through Vapotherm's adult cannulae, would purge the anatomical reservoir of the upper airway in the window of time between breaths. 

Vapotherm's humidification system is specifically designed to tolerate a high back pressure in the humidification cartridge that is generated by passing these flow rates through small bore cannulae that result in the appropriate flow velocities (turbulent energy).  Since 2000, Vapotherm HVNI has been used extensively and has been well studied and the clinical impact of this ventilation effect using Vapotherm's conventional cannula line is well described  A multi-center recent randomized clinical trial also demonstrated the noninferiority of HVNI to NIPPV in the treatment of undifferentiated respiratory distress for patients presenting to the Emergency Department.  As Vapotherm leads the innovation of new cannulae for the purpose of HVNI, we seek to evaluate the ability of these cannulae to impact ventilatory work effort on dyspneic patients. The goals of the current study are to: (1) evaluate if next generation dual prong (Prosoft) cannulae provide comparable dyspneic relief among hypercapnic adults with accompanying dyspnea compared to current legacy (control) cannula design, and (2) assess if next generation Solo (Unicorn) cannulas at lower flows provide comparable dyspneic relief among hypercapnic adults with accompanying dyspnea compared to current legacy to Dual-prong cannula (Prosoft) design.

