## **II. Overall Study Objective**

The **overall objective** of this study is to evaluate the ability of HVNI next generation Prosoft nasal cannula designs to effect ventilation and related physiological responses relative to the conventional legacy cannula design, with which there are published clinical outcomes data.

The **hypothesis**: The next generation nasal cannula designs (Prosoft and Unicorn) will be comparable at relieving patient dyspnea while on HVNI, when compared to the conventional legacy cannula.

To test this hypothesis, the study will be conducted with the following specific aims:

Aim #1: Primary Outcome. The primary endpoint is the patient's targeted relief of dyspnea, as measured by the modified Borg scale (rated perceived dyspnea [RPD]) for each cannula design tested.

Aim #2: Secondary Outcomes. The secondary endpoints evaluate the patient vital signs (heart rate [HR], respiratory rate [RR], blood pressure [BP]), arterial oxygen saturation (SpO2), and arterial CO2 as measured by a transcutaneous CO2 device (TcPCO2). These measurements will be compiled for each cannula design tested.

Aim #3: Tertiary Outcomes. The tertiary endpoints evaluate both patient and clinician perception assessment scores. For patient perception/satisfaction these endpoints include: (1) relief of symptoms, and (2) comfort/tolerance. For clinician perceptions these endpoints include: (1) technical/clinical difficulties, (2) patient comfort & tolerance, (3) ease of use, (4) monitoring & support for therapy, and (5) expected/perceived patient outcomes.

These **endpoints** will establish equivalence of outcomes between the legacy cannula and the new cannula designs (both Unicorn and Prosoft) in terms of the ability to relieve dyspnea in adult hypercapnic patients experiencing dyspnea.

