## Sample Size:

To provide a sufficiently powered sample dataset, we will enroll up to 32 subjects to complete this study on nasal cannula designs, with a calculated sample size of N=26 plus a 20% failure/fallout rate. This will provide sufficient data to adequately inform on the study objectives.

This sample size was estimated through use of references that (1) approximated minimal clinical important difference of dyspnea (modified Borg scale) and (2) approximated expected standard deviation of prior datasets measuring dyspnea. Estimated minimal clinical important difference of dyspnea was determined to be a difference value of 2 in modified Borg for dyspnea. In reviewing publications from Roca 2010 and Schwabbauer 2014, it was estimated that a value of 2 to 3 was suitable for the standard deviation of dyspnea for the modified Borg scale. Therefore, for this study, using the paired t-test sample size calculation, with an expected difference of 2, and an expected standard deviation of 3, using a desired power of 90% with alpha=0.05, the sample size is estimated at 26 to show if the data may or may not have any difference.

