#### **VI. Study Procedures**

This study is non-blinded by necessity, since the difference in cannulas can be perceived by both the clinician and patient. Patients may not know the difference between legacy and next generation cannulae, except in case of the Unicorn cannula design (as it employs a single-nasal prong). The next generation cannulae will be order-randomized after the conventional legacy cannula is used during the control evaluation. The study is a crossover design trial that will measure the ventilatory and comfort performance of nasal cannula design, specifically the effect on relief of dyspnea as demonstrated by RPD assessment, and measurement by TcPCO2 device. In addition, patient physiologic outcomes (e.g. HR, RR, BP, SpO2), and patient & clinician assessment scores will be assessed and documented. Figure 1 illustrates a flowchart of overall study procedures.

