#### Screening, Enrollment, & Management

Upon screening, subjects will be asked to participate in this study, and if so, they will provide informed consent prior to enrollment. During screening, patient will be evaluated for nostril aperture areas, which will accommodate the various cannula designs without occluding greater than 50% of the aperture area of a nostril by any cannula design (per inclusion criteria #2). Subjects are instructed that if at any time during the study that they wish to discontinue the study, they are free to stop the test and discontinue study participation. All study procedures will be explained to the subject.

Upon enrollment, appropriate study data will be collected (see below under Data Collection), including patient demographics (e.g. age, gender, ethnicity, race), anthropometrics (e.g. weight, height, BMI, and applicable medical history including a detailed focus on the patient's current respiratory status (LTOT user, positive-airway pressure therapy user, current respiratory therapy). Subjects will be managed by routine care while study data is captured as shown in the timeline below (Table 1). All decision making for patient participation will be made per standard practice at the trial site, relying on the judgment of the medical staff. Using cards coded to trial patient number, the two next generation test cannulae will be order-randomized and that randomization will be determined by the clinician or study staff opening sequential numbered opaque envelopes directing such randomization. Time required from screening to the end of the study, is estimated to be two hours and fifteen minutes.

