## VIII. Statistical Analysis

The data analysis will be "per protocol." Baseline patient demographics and characteristics will be summarized, compared, and appropriate statistical testing will be performed for the continuous and categorical variables. Assuming a non-normal data distribution for this crossover order-randomized study design, the non-parametric Wilcoxon Signed Rank Sum test will be performed with significance interval of 0.05 on all applicable variables. Parametric analytical analogues (e.g. t-test) will be use if the measurements present a normal distribution. Otherwise, for the categorical variables, the Fisher's Exact test will be performed. Data will be compared and graphed accordingly for a visual comparison with accompanied statistical notations.

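### Legacy is always tested first, so both new-versus-legacy contrasts are aliased with period and the design cannot by itself establish equivalence to legacy

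*Combined protocol and SAP*

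**What the plan says.** **Order of testing.** Section IV (Study Design) describes a crossover with randomized order, in which patients are "initially entered into the control/baseline phase with the conventional legacy cannula (control), then will be order randomized" to Unicorn or Prosoft. Section VI (Study Procedures) repeats this: "The next generation cannulae will be order-randomized after the conventional legacy cannula is used during the control evaluation". Under Screening, Enrollment, & Management, the envelopes decide only that "the two next generation test cannulae will be order-randomized". Legacy is therefore in Phase 1 for every patient.

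**Conclusion to be drawn.** Section II says that the endpoints "will establish equivalence of outcomes between the legacy cannula and the new cannula designs (both Unicorn and Prosoft", in terms of dyspnea relief. The first goal in Section I is Prosoft against legacy. The second goal is garbled where it names the comparator for Unicorn: "compared to current legacy to Dual-prong cannula (Prosoft) design". It may mean Prosoft.

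**Analysis.** Section VIII says that "the non-parametric Wilcoxon Signed Rank Sum test will be performed" at the 0.05 level, with a t-test if the data look normal. It does not mention period or sequence, and it does not say whether the baseline reading of each phase is used.

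**Safeguards.** Sections IV and VI provide a 15-minute break after Phases 1 and 2, tied to dyspnea being back at its baseline level, and a 5 to 10 minute acclimatization segment in every phase.

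**The concern.** A reader of Section IV would take the legacy comparisons to be randomized, as in an ordinary crossover. They are not. Every legacy reading comes from the first phase and every new-cannula reading from a later one. Anything that changes the response to therapy between the first exposure and later ones is therefore added to both legacy contrasts.

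A lower Borg score means less dyspnea. Improvement over the session would favour the new cannulas and could hide a real deficit, and worsening would do the reverse. A difference from legacy, or the absence of one, could then not be attributed to the cannula alone. The sentence in Section II rests on exactly these contrasts, and no section acknowledges the limit.

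**Working it through.** **1. The plan's own figure.** Section V (Sample Size) uses a paired t-test "with an expected difference of 2, and an expected standard deviation of 3", with 90% power and alpha 0.05. With a two-sided test (sidedness is not stated), the noncentral t and 3 read as the SD of the paired difference, power is 90.4% at n = 26 and 89.2% at n = 25. N = 26 reproduces, and 26 × 1.2 = 31.2 rounds up to the 32 to be enrolled. The sample size is not in dispute here.

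**2. Expected differences.** Write τL, τP, τU for the cannula effects and π1, π2, π3 for the phase effects, with no carryover.

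| Order | Prosoft − Legacy | Unicorn − Legacy | Unicorn − Prosoft |
|---|---|---|---|
| Legacy-Prosoft-Unicorn | τP − τL + π2 − π1 | τU − τL + π3 − π1 | τU − τP + π3 − π2 |
| Legacy-Unicorn-Prosoft | τP − τL + π3 − π1 | τU − τL + π2 − π1 | τU − τP + π2 − π3 |

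Averaging the two orders:

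- Prosoft − Legacy = (τP − τL) + [(π2 + π3)/2 − π1], and Unicorn − Legacy carries the same bracket.
- Unicorn − Prosoft = τU − τP, because period cancels.
- Half the difference between the two rows of the last column is π3 − π2, so that drift is estimable.

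The bracket contains π1, and π1 appears only together with τL. Adding a constant c to π1 and subtracting it from τL leaves every expected reading unchanged. For example, identical cannulas with no period effect give the same expected readings as new cannulas 0.75 points worse with a 0.75-point improvement after Phase 1. No number of patients can tell these two cases apart.

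**3. Rank check.** The model has patient, period and cannula effects. The allocation ratio is not stated, so 13 patients per order are assumed: 26 + 2 + 2 = 30 columns.

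| Design | Rank | Prosoft − Legacy | Unicorn − Legacy | Unicorn − Prosoft |
|---|---|---|---|---|
| Two planned orders, 13 each | 29 of 30 | not estimable | not estimable | estimable |
| All six orders, 5 each | 34 of 34 | estimable | estimable | estimable |

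A free period term therefore does not rescue the legacy contrasts. It only shows that they are not identified.

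**4. Illustrative size.** Assume a linear drift of d Borg points per phase. Phases 2 and 3 have mean position (2 + 3)/2 = 2.5, which is 1.5 phases after Phase 1, so the shift is 1.5 × d.

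- d = 0.25: 1.5 × 0.25 = 0.375 points, or 19% of the 2-point important difference.
- d = 0.5: 1.5 × 0.5 = 0.75 points, or 38% of it.

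The sign follows the direction of the drift. At n = 26 and SD 3 the standard error is 3/√26 = 0.59 and the 95% half-width is 2.06 × 0.588 = 1.21 points. That interval reflects sampling error only, and a period shift would come on top of it.

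**5. Can the observed drift be used as a correction?** Subtracting 1.5 times the Phase 3-minus-Phase 2 estimate assumes that the step from Phase 1 to Phase 2 equals the step from Phase 2 to Phase 3. These data cannot test that. The standard error also becomes 0.588 × √(1 + 1.5²) = 1.06, with a half-width of 2.06 × 1.06 = 2.18 points, wider than the 2-point difference of interest.

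**The case against.** **There is a practical reason for legacy-first.** The Phase 1 settings are the reference for Phases 2 and 3. This stands as an explanation of the order, but it does not make the legacy contrasts estimable.

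**The protocol limits time effects.** The pause restores resting dyspnea, and acclimatization in every phase gives the patient time to get used to the therapy. Both count: drift in resting dyspnea and part of any familiarity effect should be smaller than without them. They do not show that the response to therapy is the same on first and later exposure.

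**The size is assumed.** This is correct. The documents give no drift estimate, and drift may be nil. The figures in step 4 show scale only. The aliasing does not depend on them.

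Some stronger readings are tempting but not supported:

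- *Expectation is part of the period effect.* Section VI says "This study is non-blinded by necessity", but expectation follows from perceiving which cannula is worn, not from the phase number, and randomizing all positions would not remove it. It is a separate blinding question. The same section adds that patients may be unable to tell the new designs from legacy, apart from Unicorn.
- *The phase baselines are not comparable.* The Phase 1 text allows the patient to be on HVNI or not, but it also has the baseline taken on current oxygen therapy where applicable. The later baselines are on current or home oxygen. This is ambiguous and does not show a mismatch.
- *The whole crossover is compromised.* Unicorn versus Prosoft is randomized. If that is what the second goal in Section I intends, that goal is not affected.

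**Conclusion.** The point holds as a mismatch between design and stated conclusion. Both new-versus-legacy contrasts are aliased with period. This follows from the order of testing alone and rests on no assumed figure. Attributing a legacy difference to the cannula requires an assumption about Phase 1 against later phases that the trial cannot test.

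The practical size is unknown. Under an assumed linear drift of 0.25 to 0.5 points per phase it would be 0.38 to 0.75 Borg points in either direction. A reader might infer that the trial is biased in favour of the new cannulas, or that a wrong conclusion is likely. The documents support neither, because they give no size or direction for drift.

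The plan should be changed, but the data remain useful. What has to give way is the claim that the endpoints will establish equivalence to legacy.

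**What to change.** **1. Add to Sections IV and VIII:**

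> Only Unicorn versus Prosoft is a randomized comparison. Because legacy is always used in Phase 1, each new-versus-legacy comparison is a fixed-sequence within-patient comparison confounded with period. It will be reported with a 95% confidence interval and will not by itself be taken to establish equivalence.

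**2. Amend the equivalence sentence in Section II to match,** for example by saying that the endpoints will describe how dyspnea relief with each new design compares with legacy in this fixed sequence.

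**3. Report the Phase 3-minus-Phase 2 difference descriptively,** as limited evidence on drift that cannot be carried back to Phase 1 without an assumption.

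These three items cost wording and one summary of data already collected. A mixed model with a period term and a 1.5 × drift correction are not recommended as remedies for the legacy bias, for the reasons in steps 3 and 5.

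**Design alternative, not cheap.** Randomizing the position of legacy would make both legacy contrasts estimable. Thirty patients, five per order, fit within the 32 planned. But the later phases take their reference settings from the legacy phase, so a separate legacy run-in would be needed. If that took one acclimatization segment and one pause, it would add 5 + 15 = 20 to 10 + 15 = 25 minutes to a session already estimated at two hours and fifteen minutes from screening to end.

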HVNI will be initiated per the initial settings identified below, after which settings will be titrated per standard practice for optimal effect. When patients are placed, the HVNI initial settings will be the following: FiO2 = level approximating the patient's prior prescription (e.g. if by nasal cannula [NC], 1LPM NC = 24%, 2LPM NC = 28%, 3LPM NC = 32%, etc.), Flow = 15 L/min, and Temperature = 35 - 37°C. Patients will be fit with a Vapotherm adult nasal cannula that will be applied by a respiratory therapist or other clinician skilled in management of HVNI. The flowrate can be decreased or increased as rapidly as necessary to alleviate respiratory distress and optimize patient comfort. Targets should be to provide relief of perceived dyspnea at an HVNI flow rate between 20 to 35 L/min (up to 40L/min). Starting temperature will be between 35 to 37°C; if patients find the gas temperature to be uncomfortable, it can be lowered as necessary down to 33 °C to enhance tolerance. The FiO2 will be set initially to approximate the likely previous dosage (see above) to initially to assure adequate oxygenation, but this should be adjusted to maintain a SpO2 > 88%.

Therapeutic Characterization will be performed 5-10 minutes after the therapy acclimatization segment is completed. This will provide the patient sufficient time to receive clinical effect of the HVNI therapy and

become sufficiently comfortable with the therapy and cannula. Once the respiratory therapist or other clinician skilled in management of HVNI deems that the HVNI settings are having a therapeutic effect, the following data will be collected (see Table 1): RR, HR, BP, SpO2, TcPCO2 and RPD (Modified Borg scale 0-10). For the RPD, the clinician will record patient scores.

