## Phase 2 - Test #1 (randomized)

This test session is represented by Phase 2 in Figure 1, where the patient is placed on HVNI therapy with the order-randomized next generation cannula designs. Phase 2 will follow four distinct segments: (1) baseline characterization, (2) therapy acclimatization, (3) therapeutic characterization, (4) patient and clinician assessment scores.

Baseline Characterization will be performed just prior to the therapy acclimatization segment of this Phase. If there is a reason the clinician does not deem the patient appropriate for the study, per inclusion/exclusion criteria, they may stop procedures during baseline characterization. Sitting down in a comfortable environment, the patient will be setup and prepared for the cannula testing with appropriate data recording devices. The patient will be ON current/home oxygen therapy at this time. While subject is at rest, the following data will be collected (see Table 1): RR, HR, BP, SpO2, TcPCO2 and RPD (Modified Borg scale 0-10). For the RPD, the clinician will record patient scores.

Therapy acclimatization (5 – 10 minutes) will be performed after the baseline characterization segment is complete, and in accordance to site SOC to maintain patient safety. The patient will be fitted with appropriately sized nasal cannula (not to exceed 50% occlusion of the nares).

- IF order-randomized to the Unicorn cannula, then use the FiO2 & one-half the Flow settings from Phase 1 as a reference for the Therapeutic Settings.
  - For nostril selection of Unicorn cannula: Ask the patient to state which nostril is easiest to breathe through. Use that nostril to place the Solo/Unicorn cannula.
- IF order-randomized to the Prosoft cannula, then use the FiO2 & the Flow settings from Phase 1 as a reference for the Therapeutic Settings.

After the designated FiO2/Flow settings are implemented and the patient is acclimatized, the following data will be collected (see Table 1): RR, HR, BP, SpO2, TcPCO2 and RPD (Modified Borg scale 0-10). For the RPD, the clinician will record patient scores. Patient perception assessment will also be evaluated at this time.

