NOTE: Should the patient or clinician deem that the therapy is not providing a comparable relief of dyspnea, then after recording the data stated above, proceed to increase titration of the flow until relief of symptoms, with attention to TcPCO2. At this time, the therapy acclimatization segment should be repeated, and data will be appropriately recorded to account for this 'settings' adjustment. This is to understand any difference in cannula efficacy between legacy design and next generation cannula, designs.

Therapeutic Characterization will be performed 5-10 minutes after the therapy acclimatization segment is completed. This will provide the patient sufficient time to receive clinical effect of the HVNI therapy and become sufficiently comfortable with the therapy and cannula. Once the respiratory therapist or other clinician skilled in management of HVNI deems that the HVNI settings are having a therapeutic effect, the following data will be collected (see Table 1): RR, HR, BP, SpO2, TcPCO2 and RPD (Modified Borg scale 0-10). For the RPD, the clinician will record patient scores.

Patient & Clinician Perception Assessment will be performed by the clinician or therapist performing this phase's testing procedures. Immediately following the completion of this phase, as soon as possible, the continuous Visual Acuity Scale (VAS) will be completed for each of the five endpoints for clinician assessment and the two endpoints for the patient assessment. For the patient perception these include: (1) relief of symptoms, and (2) comfort/tolerance. For the clinician perception these include: (1) technical/clinical difficulties, (2) patient comfort & tolerance, (3) ease of use, (4) monitoring & support for therapy, and (5) expected/perceived patient outcomes.

**Upon completion of this phase**, the testing will pause for 15 minutes, until patient has returned to baseline dyspnea, prior to continuing with the next nasal cannula design test. During this pause the patient will not perform known to worsen dyspnea. During the pause the patient will continue with their current oxygen therapy.

Phase 3 - Test #2 (randomized)

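### Two sections give different rules for changing flow and FiO2 in the test phases, and the analysis does not say which reading counts once settings have changed

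*Combined protocol and SAP*

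**What the plan says.** Section IV (Study Design) says that "Titration of therapy (Flow/FiO2) is only expected during Phase 1 (or in the event the patient decompensates and needs adjustment". It also places the final data for each cannula at the therapeutic characterization and says that respiratory interventions are tracked.

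Section VI, Phase 2, sets the starting point for each test cannula. For Unicorn, staff "use the FiO2 & one-half the Flow settings from Phase 1"; for Prosoft, they "use the FiO2 & the Flow settings from Phase 1". Both are described as reference values rather than fixed settings. A reading follows once the patient has acclimatized. A note then adds a further step: "Should the patient or clinician deem that the therapy is not providing a comparable relief of dyspnea", staff record the data and "proceed to increase titration of the flow until relief of symptoms, with attention to TcPCO2". After that "the therapy acclimatization segment should be repeated, and data will be appropriately recorded to account for this 'settings' adjustment". Phase 3 repeats Phase 2.

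Under Phase 1, Section VI aims for relief "at an HVNI flow rate between 20 to 35 L/min (up to 40L/min", and of the initial FiO2 it says "but this should be adjusted to maintain a SpO 2 > 88" (percent).

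Section II makes the Borg dyspnea score (RPD) primary, makes SpO2 and TcPCO2 secondary, and says the endpoints will establish equivalence with the legacy cannula. Table 1 collects flow and oxygen at all three measured segments. Section VIII specifies a Wilcoxon signed-rank test, or a t-test if the data look normal. It says nothing about changed settings.

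**The concern.** A clinician in Phase 2 or 3 can follow Section IV or the Phase 2 note and act differently on the same patient. That makes handling depend on site and operator.

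The statistical problem follows from the timing. Flow is increased until symptoms are relieved, and only then is the cannula's final record taken. If that record is analysed, a cannula that relieved less dyspnea at its assigned settings can end the phase with a score close to legacy. A difference in the cannula then appears as a difference in flow, which no planned test examines. The error runs toward no difference, the result the study hopes to show. Unicorn is the most exposed, because the question asked of it is whether it works at lower flow.

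**Working it through.** No figure in the plan bears on this point, and its sample size of 26 plays no part. The check sets the texts side by side.

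| | Section IV | Phase 2 note (also Phase 3) | Phase 1 text |
|---|---|---|---|
| Trigger | Decompensation | Opinion of patient or clinician that relief falls short | Relief of dyspnea; SpO2 |
| Setting changed | Flow and FiO2 | Flow only, upward | Flow and FiO2 |
| Measure named | None | TcPCO2 | SpO2 above 88% |
| Flow range | None | None stated | 20 to 35, up to 40 L/min |
| Applies to test phases? | Yes | Yes | Not stated |

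**Step 1: three patients.**
- A stable patient on Unicorn reports less relief than on legacy. Section IV expects no change; the note raises flow. This is the direct conflict.
- A patient has comparable relief but an SpO2 of 88% or lower. The note is not triggered. Section IV turns on whether this is decompensation. The Phase 1 text acts only if it carries over; otherwise site standard of care governs.
- A patient on Prosoft, carried over at 40 L/min, has poor relief. The note raises flow. The Phase 1 target ends at 40 L/min, if it applies.

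**Step 2: does carry-over matter?** Halving the Phase 1 target gives the Unicorn reference flow: 20/2 = 10, 35/2 = 17.5 and 40/2 = 20 L/min. The halved range of 10 to 17.5 L/min lies below the lower end of the target, 20 L/min. If the Phase 1 target carries over, it disagrees with the half-flow instruction. If it does not, the test phases have no stated flow range or SpO2 threshold. The text must settle this either way.

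**Step 3: the order of readings.** Carried-over settings, acclimatization reading, judgement on relief, flow increase, repeated acclimatization, then therapeutic characterization. Let D0 be the mean test-minus-legacy Borg difference at the carried-over settings, p the share of patients adjusted, and c the mean Borg reduction that the adjustment produces in them. Leaving aside any drift over time, the end-of-phase difference is

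D1 = D0 − p × c.

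Flow is raised only until relief, so c should be positive. When the test cannula is worse (D0 above zero), D1 then lies below D0 and the shortfall is understated. The documents give neither p nor c, so the amount cannot be calculated.

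**Step 4: SpO2.** The note leaves FiO2 alone. FiO2 could still differ between phases by three routes: the decompensation exception in Section IV, the loose status of the carried-over settings as reference values, or the Phase 1 SpO2 target if it carries over. By any of these, similar SpO2 values could reflect different FiO2.

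**The case against.** The strongest reply is that Section IV is an overview stating an expectation, not a prohibition, while the note is the working procedure. The Phase 1 text belongs to Phase 1 and gives a target. FiO2 is carried forward and the note changes flow only. SpO2 is read at every measured segment, test-phase acclimatization follows site standard of care for safety, and flow and oxygen are on the case report form.

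Much of this stands, and it rules out stronger readings that a reader might draw:
- It is not a three-way contradiction. The conflict is between Section IV and the note; for the Phase 1 text, only its reach is unclear.
- SpO2 is not ignored in care. It is missing only from the note's written rule.
- The documents do not treat 40 L/min as a hard cap.
- The plan does not intend to compare SpO2 across adjusted FiO2. A worked SpO2/FiO2 example with assumed values would only return the FiO2 ratio put into it.

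The reply does not remove the conflict of triggers: an expectation limited to decompensation and an instruction that acts on opinion still lead to different conduct. Nor does recording settings solve the analysis, because Section VIII never uses them. The note says its extra record is there to show differences between designs, yet no analysis draws on that record.

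**Conclusion.** The point holds in this form. Section IV and the Phase 2 note differ in trigger and in scope, and the reach of the Phase 1 targets is unstated. For the Borg score and TcPCO2, end-of-phase values can be drawn together by the flow increase that the note itself prescribes. For SpO2, masking through FiO2 is possible, with unknown frequency.

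The direction, toward no difference when a test cannula is worse, rests on two assumptions: that the end-of-phase reading is the one analysed, as Section IV suggests but Section VIII does not state, and that raising flow gives at least some relief. The size is unknown. It should be corrected, since it touches the primary endpoint and the remedy uses data already planned. Nothing here says which clinical rule is right.

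**What to change.** **Protocol.** Section IV, the Phase 1 settings text and the Phase 2 note must be reconciled into one statement covering all three phases: what prompts a change, which setting may change, and whether the Phase 1 SpO2 and flow targets apply in the test phases. The investigators choose the rule. No new order of recording and adjusting is asked of staff when FiO2 is changed.

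**Section VIII.** Add text to this effect:

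*For RPD, TcPCO2 and SpO2, the cannula comparison uses the therapeutic-characterization reading if flow and FiO2 stayed at the values carried over from Phase 1. If either was later changed, it uses the acclimatization reading taken at the carried-over values, and the end-of-phase reading is reported alongside. SpO2 is presented with FiO2, with SpO2/FiO2 as a supportive measure. The number of patients with changed flow and with changed FiO2 is given for each cannula.*

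The section should also say how a patient is handled if a setting was changed before the acclimatization reading, since no reading at the carried-over values then exists.

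**Cost.** Wording, one derived variable and a short table, all from data already in Table 1. The drawback is that adjusted patients contribute a reading from an earlier time point than the others. A sensitivity analysis using the acclimatization reading for every patient in every phase would show whether that matters, and needs no further data.
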